6.4.3.2 AEs and SAEs

AEs will be summarized using MedDRA System Organ Class and preferred terms. Tables will show by treatment group the number and percentage of participants experiencing an AE within a System Organ Class or within preferred term category by severity or by relationship to study product. For the calculations in these tables, a participant with multiple AEs within a category will be counted once under the maximum severity or the strongest recorded causal relationship to study product. Formal statistical testing comparing groups is not planned since interpretation of differences must rely heavily upon clinical judgment.

A listing of SAEs reported to the DAIDS Regulatory Support Center (RSC) Safety Office will provide details of the events including severity, relationship to study product, time between onset and last vaccination, and number of vaccinations received. A separate listing will do the same for AEs of special interest (AESI). AESI for this protocol include but are not limited to potential immune-mediated disorders; a sample list of AESI is provided in Appendix J. These listings will be submitted to the FDA in all annual reports and clinical trial reports.

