The incidence of unsolicited AEs ranged from 78.3% to 83.3%. The most frequently reported symptoms were upper respiratory tract infections and headache, followed by injection site induration, injection site pruritus and pharyngeal pain. Less than half unsolicited symptoms were causally related to vaccination (incidence between 31.7% and 36.7%). The most frequent symptoms causally related to vaccination were administration site reactions (injection site induration, pruritus or warmth) and asthenia. Few grade 3 or grade 3 related symptoms occurred: 18 subjects (incidence between 6.7% and 13.3%. according to group) experienced grade 3 unsolicited symptoms, among which a majority were non-related infectious conditions (cystitis, gastroenteritis, otitis, pyelonephritis, tonsillitis, tooth abscess, upper respiratory tract infection and vaginal candidiasis). 6 of them had symptoms considered to be causally related to vaccination (lymphadenopathy, palpitations, application site hyperesthesia, asthenia, muscle rigidity, headache, and tremor).

No significant changes in laboratory parameters (hematology, biochemistry, urinalysis) and vital signs were observed throughout the study.

PRO HIV-005 evaluated an HIV vaccine candidate consisting of a recombinant fusion protein (F4) containing 4 HIV-1 clade B antigens (Gag p24, Pol-RT, Nef, and Gag p17) adjuvanted with AS01B in 3 different doses: 10, 30, and 90mcg. Each dose of the AS01B-adjuvanted vaccine candidate was administered twice in a group of 50 subjects, following a Month 0 and Month 1 schedule. Three control groups of 10 subjects received a dose of 10, 30 or 90 mcg F4 in water for injection (WFI).

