5.1 Primary objectives and endpoints

Primary objective 1

• To evaluate the safety and tolerability of DNA and/or different doses of clade C bivalent gp120 protein with either MF59 or AS01_B adjuvant in various regimens in HIV uninfected healthy adults.

Primary endpoints 1

- Severe local and systemic reactogenicity signs and symptoms (pain, tenderness, erythema, induration, fever, malaise/fatigue, myalgia, headache, nausea, vomiting, chills, arthralgia) up to 7 days after each vaccine dose
- AEs by body system, Medical Dictionary for Regulatory Activities (MedDRA) preferred term, severity, and assessed relationship to study products up to 30 days after each vaccine dose
- SAEs, AESIs, and new chronic conditions (requiring medical intervention for \geq 30 days) throughout the study
- Laboratory measures: white blood cells (WBC), neutrophils, lymphocytes, hemoglobin, platelets, alanine aminotransferase (ALT), aspartate aminotransferase (AST), alkaline phosphate (ALP), and creatinine at baseline and following vaccinations
- AEs leading to early participant withdrawal or early discontinuation of study products administration throughout the study.

Primary objective 2

• To evaluate the systemic immune responses at the Month 6.5 timepoint (2 weeks after the 4th vaccination) of clade C DNA, bivalent gp120 protein/MF59, and/or bivalent gp120 protein/AS01_B in each vaccine regimen

Primary endpoints 2

- HIV-specific total IgG binding antibody response breadth and magnitude as assessed by multiplex assay.
- Anti –V1/V2 scaffold IgG binding antibody responses as assessed by multiplex assay.
- Neutralizing antibody responses against HIV-1 isolates.
- HIV-specific CD4+ and CD8+ T-cell responses as assessed by flow cytometry.

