6.4 Statistical analyses

This section describes the final study analyses, unblinded as to treatment group assignment. Data from enrolled participants will be analyzed according to the initial randomization assignment regardless of how many vaccinations they received. In the rare instance that a participant receives the wrong treatment at a specific vaccination time, the Statistical Analysis Plan (SAP) will address how to analyze the participant's safety data. Analyses are modified intent-to-treat analysis in that individuals who are randomized but not enrolled do not contribute data and hence are excluded. Because of blinding and the brief length of time between randomization and enrollment—typically no more than 4 working days—very few such individuals are expected.

Analyses for primary endpoints will be performed using SAS and R. All other descriptive and inferential statistical analyses will be performed using SAS, StatXact, or R statistical software.

No formal multiple comparison adjustments will be employed for multiple safety endpoints, multiple primary immunogenicity endpoints, or secondary endpoints. However, multiplicity adjustments will be made for certain immunogenicity assays specified in the SAP, when the assay is viewed as a collection of hypotheses (eg, testing multiple peptide pools to determine a positive response).

Data from HVTN 108 and 111 will be combined to assess the safety and immunogenicity of the MF59 regimens. Data from these studies may be evaluated with data from other phase 1/2a studies within the P5 partnership HIV vaccine program. Comparable eligibility criteria and validated assays for primary immunogenicity endpoints will be used to mitigate the potential bias introduced by combining data across studies conducted over an extended period of time.

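### AE tables give severity and relationship separately, so participants with a non-serious grade 3/4 related AE generally cannot be counted by regimen from the planned output

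*Combined protocol and SAP*

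**What the plan says.** Section 5.1 lists among the primary safety endpoints "AEs by body system, Medical Dictionary for Regulatory Activities (MedDRA) preferred term, severity, and assessed relationship to study products", collected up to 30 days after each dose. Section 6.4.3.2 describes how these are reported: participants per treatment group with an AE "within a System Organ Class or within preferred term category by severity or by relationship to study product". The counting rule is that "a participant with multiple AEs within a category will be counted once under the maximum severity or the strongest recorded causal relationship to study product". No formal testing between groups is planned.

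The same section plans two event-level listings. The SAE listing "will provide details of the events including severity, relationship to study product, time between onset and last vaccination, and number of vaccinations received", and the AESI listing has the same content. Treatment group is not named as a field in either. No listing of other AEs is described.

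Section 7.3.3 makes related grade 3 clinical AEs (with exceptions), related grade 4 AEs and confirmed related grade 3/4 laboratory abnormalities grounds for stopping an individual's vaccinations. Table 11-1 has four rows. Three concern SAEs. The fourth sends related grade 3 or 4 AEs, other than subjective reactogenicity symptoms, to prompt review by the safety review team.

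**The concern.** A table of worst severity and a table of strongest relationship are two one-way summaries of a two-way classification. A participant shown as severe in one and as related in the other may have had one event that was both, or two events that were each only one. Even if nobody has more than one AE, the two tables do not show whether the severe participants are the related ones.

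SAEs and AESIs escape the problem because each listed event carries both attributes. Non-serious, non-AESI events do not. Safety is one of the two grounds on which regimens are to be selected for phase 2b testing (section 4.1). A final report built to this plan would give no count by arm of severe unsolicited events that investigators attributed to the product.

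**Working it through.** **1. The plan's own safety figures.** With n = 50 (section 6.1.1), the chance of at least one event at a true rate of 4.5% is 1 − 0.955^50 = 0.900, as stated. The score interval, with p = x/n and z = 1.96, is

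[p + z²/2n ± z√(p(1−p)/n + z²/4n²)] / (1 + z²/n).

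It gives 0.0% to 7.1% for 0/50 and 4.3% to 21.4% for 5/50, matching Table 6-2. No figure in the plan is in dispute.

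**2. Can the joint count be recovered?** In one category let A be the participants with any AE, S those at severe or worse, R those with a related AE, and J those with a single AE that is both.

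- With one AE per participant, J lies between max(0, S + R − A) and min(S, R).
- With several AEs per participant, the lower limit falls to 0 whatever S, R and A are, because each participant counted in both tables may have had a severe unrelated event and a mild related one.

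Assumed illustration, n = 50, A = 40, S = 6, R = 20:

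- Data set 1: 6 participants with a severe related AE, 14 with a mild related AE, 20 with a mild unrelated AE. J = 6.
- Data set 2: the same, except that the 6 each have a severe unrelated AE and a mild related AE in that category. J = 0.

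Both give identical planned tables. The answer is 12% (score 95% CI 5.6 to 23.8) in one and 0% (0.0 to 7.1) in the other. The count is fixed only in special cases: J = 0 if a row has no severe or no related participants, or, with one AE each, S = 1, R = 3, A = 3 gives J = 1.

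**3. A plausible size.** Section 4.8.3 describes a reference study of three adjuvant systems, 60 participants each. Grade 3 unsolicited symptoms occurred in 18 participants, and "6 of them had symptoms considered to be causally related to vaccination". The group range of 6.7% to 13.3% is 4/60 to 8/60, which supports a denominator of 3 × 60 = 180.

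| Quantity | Reference study | Scaled to n = 50 |
|---|---|---|
| Grade 3 unsolicited (S) | 18/180 = 10.0% | 5 |
| Related unsolicited, any grade (R) | 31.7% to 36.7% | 15.9 to 18.4 |
| Any unsolicited (A) | 78.3% to 83.3% | 39.2 to 41.7 |
| Grade 3 and related (J) | 6/180 = 3.3% | 1.7 |

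Bounds on J from S, R and A alone: lower max(0, 5 + 18 − 39) = 0, upper min(5, 16) = 5. The two tables would be consistent with 0/50 (0.0 to 7.1) up to 5/50 (4.3 to 21.4). In the reference study, 12 of the 18 grade 3 participants (67%) were outside the related group, so the severity table alone is a poor guide to the related count.

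**4. Rows versus participants.** This calculation is for all categories together. Within a single SOC or preferred-term row the numbers are smaller, and some rows are determined. Rows cannot be added into a participant count, because one person may appear in several, and 6.4.3.2 describes no overall row.

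**The case against.** A reader might infer three stronger things, and the documents support none of them.

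- *That the safety rules rest on these tables.* They do not. Table 11-1 runs on immediate site notification, and section 11.4.1 describes daily event-level review. The rows on related SAEs, including the immediate pause, concern events in the SAE listing. The Safety Monitoring Board also sees AE data unblinded by arm about every 4 months (section 11.1.2).
- *That the count cannot be obtained at all.* Every collected AE goes to the data centre on a CRF (section 11.2.2), and the endpoint calls for both attributes. What is missing is a planned table.
- *That unlike events are merged and regimen differences hidden.* The once-per-participant rule works within a SOC or preferred term. A severe unrelated infection and a mild related itch would ordinarily sit in different rows, each correctly described.

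There is also partial cover elsewhere. Severe reactogenicity is tabulated by severity and group (6.4.3.1), and vaccination discontinuations by reason and group (6.4.3.4). The second is only a proxy: 7.3.3 has exceptions, continuation may be allowed after a laboratory abnormality, and an event after the fourth dose leaves no vaccination to stop.

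The reference figures are also rough. They pool three adjuvant groups, two of them AS02 formulations not used here, and no AS01B-specific related count is given. Finally, the protocol refers to a separate SAP that may contain such a table, although the places that cite it defer other matters to it.

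These points stand and limit the finding. None supplies the by-regimen count for non-serious severe related AEs.

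**Conclusion.** The point holds as a gap in final by-arm reporting. From the output described in 6.4.3.2, the number of participants per regimen with a non-serious, non-AESI grade 3/4 AE assessed as related is generally not identified, although 5.1, 7.3.3 and one row of Table 11-1 all make the combination relevant. At reference-study rates the uncertainty is 0 to 5 of 50 participants, against about 1.7 expected.

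That size assumes the pooled 180-participant rates carry over to a group of 50. Groups 1 and 4 enrol 30 here and are pooled with HVTN 111 to 60. The logical gap does not depend on those rates. The conclusion is limited to the text supplied. No monitoring or participant-safety process is impaired, and the change is a free improvement.

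**What to change.** In section 6.4.3.2:

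- Add a table by treatment group of participants by maximum severity among AEs assessed as related: an overall row first, then SOC and preferred term. A participant counts as severe and related only if a single AE is both. Keep the planned severity and relationship tables beside it.
- Give a score 95% CI only for the overall grade 3 or higher related row. Most SOC and preferred-term cells would be 0/50 (0.0 to 7.1) or 1/50 (0.4 to 10.5), so intervals there would add little.
- Name treatment group as a field in the SAE and AESI listings. Section 6.4 already makes the final analyses unblinded by group.

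The cost is one table shell on data already collected, and a table that will be sparse. No procedure, sample size or safety rule changes.

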6.4.3.3 Local laboratory values

Box plots of local laboratory values will be generated for baseline values and for values measured during the course of the study by treatment group and visit. Each box plot will show the first quartile, the median, and the third quartile. Outliers (values outside the box plot) will also be plotted. If appropriate, horizontal lines representing boundaries for abnormal values will be plotted.

For each local laboratory measure, summary statistics will be presented by treatment group and timepoint, as well as changes from baseline for postenrollment values. In addition, the numbers (percentages) of participants with local laboratory values recorded

as meeting Grade 1 AE criteria or above as specified in the DAIDS AE Grading Table (see Section 11.2) will be tabulated by treatment group for each postvaccination timepoint. Reportable clinical laboratory abnormalities without an associated clinical diagnosis will also be included in the tabulation of AEs described above.

6.4.3.4 Reasons for vaccination discontinuation and early study termination

The number and percentage of participants who discontinue vaccination and who terminate the study early will be tabulated by reason and treatment group.

6.4.4 Immunogenicity analysis

6.4.4.1 General approach

For the statistical analysis of immunogenicity endpoints, data from enrolled participants will be used according to the initial randomization assignment regardless of how many injections they received. Additional analyses may be performed, limited to participants who received all scheduled injections per protocol. Assay results that are unreliable, from specimens collected outside of the visit window, or from HIV-infected participants postinfection are excluded. Since the exact date of HIV infection is unknown, any assay data from blood draws 4 weeks prior to an infected participant's last seronegative sample and thereafter may be excluded. If an HIV-infected participant does not have a seronegative sample postenrollment, then all data from that participant may be excluded from the analysis.

For each of the 11 primary endpoints listed in Table 6-3, response rates will be analyzed by tabulating the frequency of positive response for each endpoint and treatment group at each timepoint for which an assessment is performed. For CD4+ and CD8+ T-cell response, response rates to the individual peptide pools will also be calculated. Crude response rates will be presented with their corresponding 95% confidence interval estimate calculated using the score test method [73]. For secondary and exploratory assay endpoints, response rates and 95% confidence intervals will be calculated if appropriate for the endpoint. Criteria for a positive response for an assay will be described in the SAP.

All of the primary assays, and likely some of the secondary assays, will have quantitative assay data, including IgG binding antibody magnitude, neutralizing antibody titers, area under the magnitude-breadth curve [AUC-MB] for the neutralizing antibody assay, and percentage of positive cells from the ICS assay. Quantitative data will be displayed as graphical and tabular summaries of the distributions by antigen, treatment group, and timepoint. For all primary and secondary immunogenicity endpoints, box plots and plots of estimated reverse cumulative distribution curves will be presented by group.

Formal statistical comparisons between individual arms is not the primary objective of the trial, although these are likely to be made to better understand the effect of adjuvants on immune response and the effect of dose for arms adjuvanted with AS01_B. For comparisons in which the response rate for 1 of the groups is low (eg, $\leq 20\%$ for the class), statistical testing will use Fisher's exact test comparing the 2 response rates as most of the continuous data readouts would be left censored at the lower limit of detection. For comparisons in which the response rates for both groups are high (eg, $\geq 75\%$), the difference between groups will be tested using the continuous readouts with a nonparametric Wilcoxon rank sum test if the data are not normally distributed and with a 2-sample t-test if the data appear to be normally distributed.

HVTN 108, Version 2.0 / August 8, 2016

Some immunologic assays have underlying continuous or count-type readout that are dichotomized into responder/nonresponder categories (eg, CD4+ T cell response). If treatment group differences for these assays are best summarized by a mixture model of response rates and magnitudes, then Lachenbruch's test statistic [74] will be used to evaluate the composite null hypothesis of equal response rates in the 2 groups and equal response distributions among responders in the 2 such groups. This test statistic equals the square of a binomial Z-statistic for comparing the response rates plus the square of a Wilcoxon statistic for comparing the response distributions in the subgroup of responders. A permutation procedure is used to obtain a 2-sided p-value. For estimation, differences in response rates between groups will be estimated using the methods described above, and in the subgroup of positive responders, differences in location parameters between groups will be estimated using the methods described above.

Based upon previous HVTN trials, missing 15% of immunogenicity results for a specific assay is common due to study participants terminating from the study early, problems in shipping specimens, or low cell viability of processed PBMCs. To achieve unbiased statistical estimation and inferences with standard methods applied in a complete-case manner (only including participants with observed data in the analysis), missing data need to be missing completely at random (MCAR). Following the most commonly used definition, MCAR assumes that the probability of an observation being missing does not depend on any participant characteristics (observed or unobserved). When missing data are minimal (specifically, if no more than 20% of participants are missing any values), then standard complete-case methods will be used, because violations of the MCAR assumption will have little impact on the estimates.

If a substantial amount of immunogenicity data are missing (at least 1 value missing from more than 20% of participants), then using the methods that require the MCAR assumption may give misleading results. In this situation, analyses of the immunogenicity endpoints at a specific timepoint will be performed using parametric generalized linear models fit by maximum likelihood. These methods provide unbiased estimation and inferences under the parametric modeling assumptions and the assumption that the missing data are missing at random (MAR). MAR assumes that the probability of an observation being missing may depend upon the observed responses and upon observed covariates, but not upon any unobserved factors. Generalized linear models for response rates will use a binomial error distribution and for quantitative endpoints, a normal error distribution. For assessing repeated immunogenicity measurement, linear mixed effects models will be used. If the immunological outcomes are left- and/or right- censored, then the linear mixed effects models of Hughes [75] will be used, because they accommodate the censoring. In addition, secondary analyses of repeated immunogenicity measurements may be done using weighted GEE [76] methods, which are valid under MAR. All of the models described above will include as covariates all available baseline predictors of the missing outcomes.

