6.1 Accrual and sample size calculations

Recruitment will target enrolling 334 healthy, HIV-uninfected adult participants ages 18-40 in Southern Africa and the United States. Participants will be randomized to 8 treatment groups (7 vaccine groups and 1 placebo group). Vaccine groups 1-3 share the same DNA prime and test 3 different boosts consisting of DNA coadministered with a protein/adjuvant combination (gp120 proteins at 100 mcg with MF59 adjuvant, gp120 proteins at 100 mcg with AS01_B, or gp120 proteins at 20 mcg with AS01_B) at 2 timepoints. In groups 4-6 the DNA is coadministered with 1 of the protein/adjuvant combinations at 3 timepoints. An additional vaccine group (group 7) will test the proteins alone at the 20 mcg dose adjuvanted with $AS01_{B}$ administered at 3 timepoints. Groups 2, 3 and 5-7 will enroll 50 participants per group. Groups 1 and 4 evaluating the proteins adjuvanted with MF59 will enroll 30 participants per group as these two vaccine regimens are also being evaluated in HVTN 111 at sites in Southern Africa (HVTN 111, n=30 per group). Evaluation of these 2 regimens will pool data from HVTN 108 and HVTN 111 for a total of 60 participants per group. The primary purpose of the placebo group (Group 8 n=24) is to ensure blinding. To ensure that both men and women will be adequately represented in the trial, the trial will enroll at least approximately 40% of each sex overall. Hence, when approximately 200 participants of 1 sex are enrolled, recruitment of persons born of that sex will stop.

Since enrollment is concurrent with receiving the first study vaccination, all participants will provide some safety data. However, for immunogenicity analyses, it is possible that data may be missing for various reasons, such as participants terminating from the study early, problems in shipping specimens, low cell viability of processed peripheral blood mononuclear cells (PBMCs) or high background. Immunogenicity data from 17 phase 1 and 2 phase 2a HVTN vaccine trials, which began enrolling after June 2005 (data as of September 2014), indicate that 15% is a reasonable estimate for the rate of missing data at Month 6.5. For this reason, the sample size calculations in Section 6.1.2 for n=50 account for 7 enrolled participants on each group having missing data for the primary immunogenicity endpoint.

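### Fisher's exact test for low-response comparisons is valid but conservative; Boschloo's exact test never loses power, gaining about 5–8 points at equal arms of about 43 and usually less otherwise

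*Combined protocol and SAP*

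**What the plan says.** Section 6.4.4.1 chooses the between-arm test by response level. "For comparisons in which the response rate for 1 of the groups is low", with 20% or less as the example, "statistical testing will use Fisher's exact test comparing the 2 response rates". The reason given is that most continuous readouts would then sit at the detection limit. When both groups respond at high rates (the example is 75% or more), a Wilcoxon or t-test on the continuous readout is used. Lachenbruch's two-part test is available where rate and magnitude are best summarised together.

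The same section says "Formal statistical comparisons between individual arms is not the primary objective of the trial", but that comparisons are likely to be made "to better understand the effect of adjuvants on immune response and the effect of dose for arms adjuvanted with AS01_B". It gives no alpha, target difference or power for them.

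On arm sizes, section 6.1 says "Groups 2, 3 and 5-7 will enroll 50 participants per group", and the calculations "account for 7 enrolled participants on each group having missing data". Groups 1 and 4 (MF59) "will enroll 30 participants per group as these two vaccine regimens are also being evaluated in HVTN 111"; their data are pooled across the two trials, with 51 evaluable expected (section 6.1.2). Section 6.4 says analyses other than those of primary endpoints will be done "using SAS, StatXact, or R statistical software".

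**The concern.** Fisher's test conditions on the total number of responders. With two small binomial samples its attainable significance levels are coarse, and the true size falls well short of the nominal level. In the low-response branch the continuous readout has been set aside, so this binary test carries the whole comparison. The unused error rate is then power given up.

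The comparisons have some weight. Section 4.3 lists the adjuvant and AS01B dose effects among the questions behind the trial programme. It also says that only one AS01B-adjuvanted protein dose per regimen will be considered for phase 2b. A dose or adjuvant effect that falls in this branch could be missed more often than necessary.

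**Working it through.** **Inputs from the protocol.** AS01B arms: 50 − 7 = 43 evaluable. Pooled MF59 regimens: 60 × 0.85 = 51 evaluable. Fisher applies when the lower rate is about 20% or less.

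**Assumptions.** Two-sided 5% level, Fisher p-value formed by table probability, and the response-rate pairs shown below. The protocol gives none of these for this test.

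**1. Reproducing the plan's own figures.** No power is stated for any Fisher comparison, so the check is on the ATP figures at the same arm size. The score interval is [p + z²/2n ± z√(p(1−p)/n + z²/4n²)] / (1 + z²/n). For 19/43, p = 0.4419 and z²/n = 3.8415/43 = 0.0893. The centre is (0.4419 + 0.0447)/1.0893 = 0.4466 and the half-width is 1.96 × √(0.005735 + 0.000519)/1.0893 = 0.1423. The interval is 30.4% to 58.9%, as in Table 6-4. A 10,000-run simulation of the ATP rule gives 80.1% power at δ = 24% (stated: at least 80%) and a largest type 1 error of 17.5% (stated: at most 18%).

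**2. Rejection regions.** For arms of n and m, let F(x, y) be the two-sided Fisher p-value with x and y responders.
- Fisher rejects when F(x, y) ≤ 0.05.
- Boschloo rejects when F(x, y) ≤ c. Here c is the largest value for which the size, max over π of Σ Bin(x; n, π) Bin(y; m, π) over the rejection region, is at most 0.05.
- Since c exceeds 0.05, every table rejected by Fisher is also rejected by Boschloo.

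All 2×2 tables were enumerated, with π on a 999-point grid.

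| Arms | Fisher maximum size | Boschloo maximum size | c |
|---|---|---|---|
| 43 v 43 | 3.18% | 4.96% | 0.0753 |
| 51 v 43 | 3.82% | 4.85% | 0.0598 |

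At 43 v 43 and a common rate of 20% or less, Fisher's size is at most 2.59%. For single tables at 43 v 43, 4 v 12 responders gives p = 0.0501 (Fisher) and 0.0335 (Boschloo), and 5 v 13 gives 0.0616 and 0.0399.

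**3. Power at 43 v 43.** Power = Σ Bin(x; n, p₁) Bin(y; m, p₂) over the rejection region. Gains are rounded from unrounded power.

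| Rates | Fisher | Boschloo | Gain |
|---|---|---|---|
| 5% v 25% | 68.1 | 74.4 | 6.3 |
| 10% v 30% | 55.2 | 63.5 | 8.4 |
| 10% v 35% | 74.2 | 80.5 | 6.2 |
| 15% v 40% | 68.3 | 74.3 | 6.0 |
| 20% v 45% | 63.6 | 70.6 | 7.0 |
| 20% v 50% | 79.6 | 84.6 | 5.0 |

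Once Fisher's power is above about 90%, the gain is about 3 points or less.

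**4. Other arm sizes, same six pairs.**
- 50 v 50: 3.5 to 5.5 points.
- 51 v 43: 2.0 to 3.7 points with the larger arm low (10% v 30% moves from 65.0 to 68.6), and 1.4 to 4.1 with the smaller arm low.
- 42 v 43: 0.1 to 2.6 points.
- 43 v 44: 1.0 to 3.1 points.
- 40 v 45: 0.0 to 0.1 points.

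The pattern is not smooth. At 41 v 43, over low rates of 5–20% with Fisher power between 30% and 80%, the gain is 2.9 to 6.4 points.

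**5. Averaging over missing data.** With two arms of 50 and independent 14% missingness (7/50), the expected gain over the six pairs is about 2.0 to 3.4 points. It is below 5 points in 78–93% of realisations.

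**The case against.** The strongest objection is that nothing here is wrong. Fisher's test controls the error rate and is standard, and these comparisons are not the primary objective. The protocol states no alpha or power for them. That stands, and it limits the point to efficiency.

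Two stronger readings are tempting, and the documents do not support either.
- **A general loss of 5–8 points.** That range fits equal evaluable arms of about 43. The number 43 is a planning allowance, and exactly 43 v 43 would occur about 2.6% of the time under the missingness model above. The pooled adjuvant comparison stays below 5 points.
- **Every adjuvant and dose comparison is affected.** Fisher is used only in the low-response branch. High-response comparisons use continuous readouts, and CD4+ T-cell response is the section's own example for Lachenbruch's test. The prior dose-dampening evidence in section 4.5.4 concerns CD4+ responses. Earlier gp120/AS01B data in section 4.5.3 show IgG1 and V1V2 antibody responses in all subjects tested, far from this branch. If more than 20% of participants have missing values, the section moves to generalized linear models.

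None of this removes the case for the change. Boschloo's test, ordered as above, is never worse than Fisher's and holds the same level.

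**Conclusion.** The point holds as a no-loss efficiency improvement for a non-primary analysis. Fisher's test is conservative at the planned sizes, with a largest size of about 3.2% at 43 v 43 and 3.8% at 51 v 43. Boschloo's test recovers about 5–8 points at moderate power for equal arms of about 43 and about 1–4 points for pooled MF59 v AS01B. The gain is mostly 0–3 points when evaluable counts differ slightly. These figures rest on the assumed two-sided 5% level, table-probability ordering and chosen rate pairs. A reader might infer a flaw in the trial's main decision rule, but the ATP assessment uses single-arm score intervals and does not involve this test.

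**What to change.** In section 6.4.4.1 and the SAP, replace Fisher's exact test with Boschloo's unconditional exact test for the low-response branch. Before unblinding, state three things: the ordering statistic (the two-sided Fisher p-value by table probability), the two-sided convention, and alpha.

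The convention matters when arms are unequal. At 43 v 26 (an unpooled MF59 arm: 30 × 0.85 = 25.5), a version built by doubling one-sided p-values loses 10.0 points to Fisher at 2% v 12%.

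Barnard's test and mid-p versions should not be offered as equivalents. Barnard's with a pooled-score statistic loses up to 1.7 points to Fisher at 43 v 42 for the pairs tried, and mid-p does not guarantee the 5% level.

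The cost is a sentence or two of text. The software already named can run the test, and no data, visit or sample-size change is needed.
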